2.2 Background

Hyperkalaemia is a potentially life-threatening electrolyte disorder and is primarily caused by renal dysfunction leading to reduced excretion of K^+ . The incidence of HK in CKD patients has been reported to range between 7.7% and 73% (Kovesdy, 2017).

In a study of approximately 36,000 patients with an estimated glomerular filtration rate (eGFR) < 60 ml/min per 1.73 m², HK was associated with increased all-cause mortality (Nakhoul et al, 2015).

Because HK can induce or worsen cardiac arrhythmias, it is associated with significantly increased mortality (Kovesdy, 2017).

Treatment of severe HK is then a medical emergency but it should be followed by continuous long-term treatment to prevent recurrence. So far, the common practice for managing chronic HK is focused on eliminating HK predisposing factors. Patients are then advised to reduce high K⁺ intake in diets but also to withdraw or reduce medications known to raise K⁺ levels. Among these medications, RAASi, for example, are commonly prescribed in patients with CKD, and are often discontinued to manage HK, in spite of their recognised cardiovascular and renal benefits in this population (Kovesdy, 2017). Furthermore, withholding RAASi may lead to incremental healthcare costs associated with poor outcomes, such as end-stage renal disease, hospitalisations due to cardiovascular causes, and cardiovascular mortality (Dunn et al, 2015).

Maintaining the use of these beneficial medications while implementing various strategies to control K⁺ balance is desirable and could be obtained by long-term use of K⁺ binders (Kovesdy, 2017). A treatment of up to 12 months with SZC utilising a dose titration scheme with the starting dose of 5 or 10 g daily, titrated to a maximum of 15 g daily or a minimum of 5 g every other day, was effective in maintaining NK in the majority of subjects in a long-term study (Spinowitz et al, 2019). However, in the US, only 0.1% of patients with a HK-related inpatient stay received a binder at discharge (Davis et al, 2019).

Hyperkalaemia is reported in less than 5% of the population, worldwide (Lederer and al, 2020) but may affect up to 10% of hospitalised patients (Rossignol et al, 2016). In addition to clinical consequences, HK is associated with increased health care costs and healthcare resource utilisation (HRU):

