- Diabetes (Yes/No, identified per Medical History eCRF using an SMQ of “Hyperglycaemia/new onset diabetes mellitus” with a narrow scope; SMQ Code: 20000041 which includes preferred terms of: Acquired generalised lipodystrophy, Blood 1,5-anhydroglucitol decreased, Blood glucose increased, Diabetes complicating pregnancy, Diabetes mellitus, Diabetes mellitus inadequate control, Diabetes with hyperosmolarity, Diabetic arteritis, Diabetic coma, Diabetic coronary microangiopathy, Diabetic hepatopathy, Diabetic hyperglycaemic coma, Diabetic hyperosmolar coma, Diabetic ketoacidosis, Diabetic ketoacidotic hyperglycaemic coma, Diabetic ketosis, Diabetic metabolic decompensation, Diabetic wound, Euglycaemic diabetic ketoacidosis, Fructosamine increased, Fulminant type 1 diabetes mellitus, Gestational diabetes, Glucose tolerance impaired, Glucose tolerance impaired in pregnancy, Glucose urine present, Glycated albumin increased, Glycated serum protein increased, Glycosuria, Glycosuria during pregnancy, Glycosylated haemoglobin abnormal, Glycosylated haemoglobin increased, Hepatogenous diabetes, Hyperglycaemia, Hyperglycaemic crisis, Hyperglycaemic hyperosmolar nonketotic syndrome, Hyperglycaemic seizure, Hyperglycaemic unconsciousness, Impaired fasting glucose, Insulin resistance, Insulin resistant diabetes, Insulin-requiring type 2 diabetes mellitus, Ketoacidosis, Ketonuria, Ketosis, Ketosis-prone diabetes mellitus, Latent autoimmune diabetes in adults, Maternally inherited diabetes and deafness, Monogenic diabetes, Neonatal diabetes mellitus, Neonatal hyperglycaemia, New onset diabetes after transplantation, Pancreatogenous diabetes, Pseudodiabetes, Steroid diabetes, Type 1 diabetes mellitus, Type 2 diabetes mellitus, Type 3 diabetes mellitus, Urine ketone body present)
- Renin-angiotensin-aldosterone system inhibitors (RAASi) use at screening (Yes/No, identified per Concomitant Medication eCRF as CMCLASCD in ('C09AA', 'C09BA', 'C09BB', 'C09BX', 'C09CA', 'C09DA', 'C09DB', 'C09DX', 'C09XA') where Start Date is prior to admission date for in-patient phase of hospital visit)
- CKD diagnosis (identified per Medical History eCRF using a LLT containing “Chronic kidney disease”)
- CKD stage (derived based on eGFR value), calculated as:
  - Grade 1 ( $eGFR \geq 90$ )
  - Grade 2 ( $60 \leq eGFR < 90$ )
  - Grade 3a ( $45 \leq eGFR \leq 59$ )
  - Grade 3b ( $30 \leq eGFR \leq 44$ )

- Grade 4 ( $15 \leq \text{eGFR} \leq 29$ )
- Grade 5 ( $\text{eGFR} < 15$ )

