#### 4.2.2.6 Subgroup Analyses

Subgroup analyses will be performed using separate logistic regression models, as per section 4.2.2.4, by age (18-64, 65-84 and  $\geq 85$  years), sex (female, male), recruitment country (France, Italy, Spain, UK, Belgium and Netherlands), presence of heart failure (Yes/No, identified per Medical History using an SMQ of “Cardiac Failure”; SMQ Code: 20000004), diabetes (Yes/No, identified per Medical History eCRF using a PT of “Type 2 diabetes mellitus”), RAASI use at screening (Yes/No, identified per Concomitant Medication eCRF as CMCLASCD in (‘C09AA’, ‘C09BA’, ‘C09BB’, ‘C09BX’, ‘C09CA’, ‘C09DA’, ‘C09DB’, ‘C09DX’, ‘C09XA’) where Start Date is prior to date of informed consent), CKD stage, without diagnosis of CKD (but eGFR  $< 90$  ml/min/1.73m^2), baseline  $K^+$  ( $5.0 < K^+ \leq 5.5$  versus  $5.5 < K^+ \leq 6.5$  mmol/L) at baseline, an alternative baseline  $K^+$  categorisation ( $5.0 < K^+ \leq 5.5$ ,  $5.5 < K^+ \leq 6.0$ , and  $6.0 < K^+ \leq 6.5$  mmol/L) and by duration of index hospitalisation ( $< 7$  days versus  $\geq 7$  days). Subgroup analyses will only be conducted providing there are 10 or more events per subgroup category.

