#### **4.2.5.5 Sensitivity Analyses of the Secondary Endpoint #3**

Three sensitivity analyses will be conducted for this secondary endpoint:

- Providing there are sufficient participants within each covariate to support the analysis, an alternative population level summary using the FAS population where the negative binomial regression model will include randomised treatment group, duration of time in study as an offset and the following baseline variables: age (as a cubic spline), sex, participant recruitment country, presence of heart failure, diabetes, RAASi use, CKD

stage, and baseline  $K^+$  ( $5.0 < K^+ \leq 5.5$  versus  $5.5 < K^+ \leq 6.5$  mmol/L) as independent variables. Baseline variables will be defined as described in section 4.2.2.6.

- A sensitivity analysis will be conducted using the mean cumulative count method (MCC) (Austin et al, 2010) if a greater than 10% difference by treatment arm in the proportion who are lost to follow-up is observed. The MCC method reflects a summarisation of all events that occur in a population by a given time. The recurring event in this analysis will be hospital admission with HK as a contributing factor. The MCC will be performed by randomised treatment group in the FAS and an estimate (95% CI) of the MCC at 90 and 180 days post discharge will be presented. A figure of the MCC by randomised treatment group with 95% CI will also be displayed. SAS Code to conduct an MCC analysis is described in sections 7.1 and 7.2.
- Alternative population: As primary estimand, but the per protocol set (PPS) will be used as the population for analysis.

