#### **4.2.13.5 Sensitivity Analyses of the Exploratory Endpoint #5**

Providing there are sufficient participants within each covariate to support the analysis, an alternative population level summary using the FAS population where the MMRM analysis will include randomised treatment group and the following baseline variables: age (as a cubic spline), sex, presence of heart failure, diabetes, RAASi use, CKD stage and baseline  $K^+$  (mild HK defined by  $5.0 < K^+ \leq 5.5$  and moderate/severe HK defined by  $5.5 < K^+ \leq 6.5$  mmol/L) as independent variables. Baseline variables will be defined as described in section 4.1.6.1.

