#### 4.2.25.2 Derivations

RAASI use at discharge is derived using the concomitant medication rescue medications eCRF as where one or more CMCLASCD in ('C09AA', 'C09BA', 'C09BB', 'C09BX', 'C09CA', 'C09DA', 'C09DB', 'C09DX', 'C09XA') where Start Date is prior to the date of randomisation and End Date is ongoing or after the date of randomisation. RAASI use at day 90 post-discharge is derived using the concomitant medication rescue medications eCRF as above where Start Date is prior to day 90 post-discharge and End Date is ongoing or after day 90 post-discharge. RAASI use at day 180 post-discharge is derived using the concomitant medication rescue medications eCRF as above where Start Date is prior to day 180 post-discharge and End Date is ongoing or after day 180 post-discharge. A RAASI dose increase at 90 and 180 days post-discharge is defined where the CMDECOD at discharge is different at 90 or 180 days or where CMDECOD at 90 or 180 matches that at discharge but the CMDOSTXT is greater than at discharge. A RAASI dose decrease at 90 and 180 days post-discharge is defined, where CMDECOD at 90 or 180 days matches that at discharge but the CMDOSTXT is less than at discharge.

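### Diabetes and RAASi use at screening each have two conflicting definitions in the SAP, and neither RAASi definition checks the stop date

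*SAP*

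**What the plan says.** **Diabetes.** SAP 4.1.6.1 has "Diabetes (Yes/No, identified per Medical History eCRF using an SMQ of" hyperglycaemia and new-onset diabetes (narrow scope, code 20000041). The terms printed there include type 1, type 2, unspecified, steroid and gestational diabetes. They also include findings such as raised blood glucose, glycosuria, ketonuria and insulin resistance. The subgroup sections for the primary endpoint (4.2.2.6) and secondary endpoint #1 (4.2.3.7) have instead "diabetes (Yes/No, identified per Medical History eCRF using a PT of" type 2 diabetes mellitus, a single preferred term.

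**RAASi use at screening.** Both versions use the same drug-class codes. SAP 4.1.6.1 counts a record "where Start Date is prior to admission date for in-patient phase of hospital visit". The subgroup list in 4.2.2.6 reads "where Start Date is prior to date of informed consent), CKD stage, without diagnosis of CKD", so its cut-off is consent. The consent cut-off recurs in 4.2.3.7, 4.2.4.7, 4.2.5.7, 4.2.6.7, 4.2.7.7 and 4.2.8.7. Neither version mentions an end date. For RAASi use at discharge, SAP 4.2.25.2 does apply one: "where Start Date is prior to the date of randomisation and End Date is ongoing or after the date of randomisation".

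**Which definition the models use.** The adjusted negative binomial models in 4.2.5.5 and 4.2.14.5 say "Baseline variables will be defined as described in section 4.2.2.6". The adjusted repeated-measures model for potassium in 4.2.13.5 says "Baseline variables will be defined as described in section 4.1.6.1". The adjusted logistic model (4.2.2.5), the adjusted Cox model and the inverse-probability-weighting model (both 4.2.3.5) cite neither section.

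Protocol 9.4.3.1 and 9.4.3.2 name diabetes and RAASi use as baseline variables without deriving them. Neither SAP section 2 nor the SAP amendment history presents the difference as intended.

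**The concern.** Two programmers could each follow the SAP faithfully and produce different diabetes and RAASi flags for the same participants. The disease-characteristics table would then describe strata that are not the ones analysed in the subgroups. In an open-label trial, leaving the choice to the programming stage also means it could be made with outcomes in view.

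For diabetes the subgroup rule is wrong on its face. It puts people with type 1 or unspecified diabetes into the comparison group labelled as not having diabetes.

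For RAASi the missing end date is a second and separate defect. Protocol 2.2 says these drugs "are often discontinued to manage HK", so stopping around an admission for hyperkalaemia is plausible in this population. RAASi down-titration counts as non-response for the primary endpoint and is itself a tested secondary endpoint with a RAASi-use subgroup (4.2.6.7). Someone who had stopped before consent and did not restart cannot have that event, yet would sit in the Yes stratum if the drug was recorded.

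**Working it through.** The SAP has no figure to reproduce here, so the check compares the definitions and classifies hypothetical participants under each.

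**Step 1. Classification.** Table means 4.1.6.1; subgroup means 4.2.2.6 and the sections that repeat its rule.

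| Participant | Table | Subgroup |
|---|---|---|
| Type 2 diabetes | Yes | Yes |
| Type 1 diabetes only | Yes | No |
| Unspecified diabetes mellitus only | Yes | No |
| Glycosuria or impaired fasting glucose only | Yes | No |
| RAASi started before admission, ongoing | Yes | Yes |
| RAASi started after admission, before consent | No | Yes |
| RAASi started before admission, stopped before consent, recorded | Yes | Yes |

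The type 2 term is on the standardised query's list, so the diabetes subgroup definition is a subset of the table definition. Changes run only from Yes to No. For RAASi the order is reversed. Protocol 1.1 places screening while the participant is already an inpatient, so consent cannot precede admission and changes run only from No to Yes. Participants in the remaining rows do not move.

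**Step 2. The end date.** The last row is Yes under both definitions, although the drug was not in use at screening. The omission therefore misclassifies former users but does not make the two definitions disagree. Under the 4.2.25.2 rule the same person is not on a RAASi at discharge unless it was restarted.

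**Step 3. Would a stopped drug be in the data?** Protocol 6.7 requires recording only of medication received at enrolment or during the study, and the protocol defines enrolment by consent. SAP 4.1.8.1 provides for prior medications with a stop date before the first SZC dose, which suggests some stopped drugs are expected. A drug stopped between consent and first dose would also meet that description, so it does not settle the matter. The end-date defect matters only to the extent that such drugs were recorded.

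**Step 4. Reach.** The primary logistic model uses treatment and country (4.2.2.4). The log-rank test is by treatment, with country added in the Cox model (4.2.3.4). The negative binomial model uses treatment and an offset (4.2.5.4). None uses diabetes or RAASi use, and these models carry the hierarchy in Table 5. The variables enter the disease-characteristics table, the multi-covariate sensitivity and additional models, the weighting model and the subgroups. Diabetes is a subgroup only in 4.2.2.6 and 4.2.3.7.

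**Step 5. Event-count thresholds.** Subgroups need 10 or more events per category. The adjusted logistic and Cox models need more than 10. For secondary endpoint #1, Protocol 9.2.2 assumes 17% and 43.2% with an event:

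- 52 per arm: 0.17 × 52 + 0.432 × 52 = 8.8 + 22.5 = 31.3 events.
- 65 per arm (130 randomised): 0.17 × 65 + 0.432 × 65 = 11.1 + 28.1 = 39.1 events.

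Taking the threshold to apply to both arms together, the smaller category must hold 10/31.3 = 32% or 10/39.1 = 26% of all events. With totals this small, moving a few participants could decide whether a subgroup or covariate is analysed. Whether it does depends on counts that the documents do not give.

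**The case against.** The best case for leaving this as minor is that no formally tested result depends on it. That stands. A reader might infer that the primary or main secondary result is at risk, and Step 4 shows that it is not.

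A reader might also infer that the missing stop date makes participants change category between table and subgroup. It cannot, because both definitions omit it. For RAASi only a start between admission and consent causes a change, and such starts may be few during an admission for hyperkalaemia. The sentence from Protocol 2.2 is general background and gives no rate for this cohort.

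It is tempting to put a percentage on the dilution of a subgroup effect. The documents do not support one. It would need the proportion of flagged users who had stopped, an assumed effect in them, and a linear scale, whereas the subgroup models estimate odds, hazard and rate ratios. For covariate adjustment in a randomised comparison, a poorly measured baseline covariate mainly costs precision.

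Finally, a reader might conclude that RAASi use at discharge should replace use at screening as the covariate. The protocol lists RAASi use among baseline variables, and SAP 3.3.1.1 sets baseline before the first inpatient SZC dose. The substitution would depart from both and is not needed to remove the inconsistency.

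It is also fair to say that 4.2.2.5 and 4.2.3.5 are unspecified rather than contradictory. But silence offers no way to choose between two live definitions, so the objection does not remove the problem.

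**Conclusion.** The conflict is real for both variables, and nothing in either document resolves it. The diabetes subgroup rule and the missing RAASi end date are faulty as written; they are not merely under-described. The consequence is limited to descriptive, sensitivity, weighting and subgroup output and to the thresholds that decide which of these are run. The number of participants affected is unknown. It depends on how many have diabetes or glycaemic terms other than type 2, how many started a RAASi between admission and consent, and whether drugs stopped before consent were recorded. The point should be corrected, but it does not threaten the formal conclusions.

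**What to change.** State one definition of each variable in SAP 4.1.6.1. Have every subgroup section and every adjusted or weighting model refer to it, including those that now cite 4.2.2.6 or nothing.

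- **Diabetes:** do not restrict it to the type 2 preferred term. Use a fixed list covering type 1, type 2, unspecified and other diabetes diagnoses. Leaving out the laboratory-finding terms narrows the current table definition, so record that choice explicitly.
- **RAASi use at screening:** use one start-date cut-off, and add the condition that the end date is missing, ongoing, or on or after consent. A start before consent fits that condition and is already the rule in seven of the eight places.
- Confirm whether RAASi stopped before enrolment were entered on the concomitant-medication form, and say so in the SAP.

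The cost is SAP wording and a change to two derivations, with the affected tables rerun. Medical-history terms and medication dates are already collected, so no new data are needed. The change should be made before database lock.

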Assuming a 20% drop-out rate from enrolment to randomisation and a 20% drop out post-discharge (post-randomisation), approximately 163 participants will be enrolled, resulting in approximately 130 participants discharged and randomised, to achieve 104 evaluable participants (52 per arm).

Note: “Enrolled” means a participant's, or their legally acceptable representative's, agreement to participate in a clinical study following completion of the informed consent process. Potential participants who are screened for the purpose of determining eligibility for the study, but are not assigned treatment in the study, are considered “screen failures”, unless otherwise specified by the protocol.

Intervention Groups and Duration:

All participants will be treated with SZC as per local label (correction and/or maintenance treatment) during the in-hospital phase. The duration of in-hospital phase will be 1 to 21 days post-enrolment; medical monitor's approval may be sought for allowing longer duration hospital stays for specific participants.

At discharge, participants who are NK (K^+ between 3.5 and 5.0 mmol/L, inclusive) and have been started on a maintenance dose for SZC will be randomised in a 1:1 ratio to one of the following arms and subsequently enter the outpatient phase:

- Arm A: Participants discharged with SZC, as per local label, to manage HK until end of outpatient phase
- Arm B: Participants discharged with SoC, as per local practice, to manage HK until end of the study.

Note: Participants intended to receive a K-binder at discharge (as per the site routine medical practice) will not be randomised and will be discontinued from the study. Still, it is allowed that participants randomised into Arm B have any K-binder prescribed at Day 7 post-discharge (or after Day 7 post-discharge), to treat confirmed HK or in case there is an increase in K^+ level since discharge that, in the investigator's opinion, requires therapy.

The duration of outpatient phase will be approximately 180 days.

After the outpatient phase, participants will enter into the follow-up phase which will last 7 days. Study drug will be discontinued for participants in Arm A. These participants will be treated as per local practice (SoC). Participants in Arm B will continue SoC treatment.

The total study duration for each participant will then be approximately 6 months.

Adjudication Committee: Yes

Statistical Methods:

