9.2.1 Primary Endpoint

For the primary endpoint a sample size estimate would calculate;

- Two group χ^2 test
- Significance level: 5% (two-sided)
- Power: 80%

- Proportions with NK (K^+ between 3.5 and 5.0 mmol/L, inclusive) at 180 days post-discharge), ([Davis et al, 2019](#); [Spinowitz et al, 2019](#)):
 - Arm A (SZC): 0.88
 - Arm B (SoC): 0.59

The above test specifics and assumptions yield a sample size of 36 participants per arm (total N = 72). Assuming a 20% drop out rate from enrolment to randomisation and a 20% drop out post-discharge (post-randomisation), a total of approximately 113 participants will be enrolled. This is exceeded by the number of participants required for the secondary endpoint sample size calculation (Section [9.2.2](#))

The above effect-size assumptions do not contemplate the potential impact of RAASi down-titration on response. Since this is expected to diminish the response rate in the SoC arm relative to the treatment arm, these conservative assumptions should provide a slight underestimate of power.

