### 4.2.2.4 Primary Analysis of Primary Endpoint

Occurrence (yes/no) will be compared between treatment groups in the FAS using a logistic regression model including response as the dependent variable and randomised treatment (reference level SoC) and participant recruitment country as an independent variable, and

will be tested using a two-sided alpha = 0.05. For participants who are assigned a non-response value, a sub table will be provided to summarize the intercurrent events, which led to this assignment, by treatment group. The common odds ratio will be derived together with the two-sided 95% confidence interval.

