#### 4.2.2.5 Sensitivity Analyses of the Primary Endpoint

The analyses of the primary endpoint will be repeated as per section 4.2.2.4 but with alternative modelling:

- Population level summary (analysis): Providing there are sufficient participants within each covariate to support the analysis, the logistic regression model will include randomised treatment group and the following baseline variables: age (as a cubic spline), sex (male/female), participant recruitment country, presence of heart failure (yes/no), diabetes (yes/no), RAASi use (yes/no), CKD stage and baseline  $K^+$  ( $5.0 < K^+ \leq 5.5$  versus  $5.5 < K^+ \leq 6.5$  mmol/L) as independent variables. Sufficient participants for a covariate to be included will be considered if there are more than 10 participants with an event in each level of the covariate.

The analyses of the primary endpoint will be repeated as per section 4.2.2.4 but the estimand will be varied:

- Intercurrent event strategy: As primary estimand, but participants needing rescue therapy for HK will follow the treatment policy strategy (i.e., regardless of the intercurrent event).
- Intercurrent event strategy: As primary estimand, participants with RAASi down-titration (including discontinuation) will follow the treatment policy strategy (e.g. regardless of the intercurrent event).
- Intercurrent event strategy: As primary estimand, but participants who die or are lost to follow-up prior to 180 days post-discharge will not be evaluated (completers analysis only).
- Hypothetical strategy: As primary estimand, but participants who are lost to follow-up after 90 days (visit 7) or who are missing  $K^+$  status at 180 days will have their  $K^+$  status at 90 days, if available, carried forward to 180 days and included in the analysis using the principle of last observation carried forward.
- COVID-19 supplementary analysis: Intercurrent events not related to COVID-19 will be treated as per section 4.2.2.4. Participants who discontinue treatment due to COVID-19 will be treated as missing (hypothetical strategy). Use of rescue therapy for HK due to COVID-19 will be considered to be non-response (composite variable strategy). RAASi down-titration due to COVID-19 (including discontinuation) will be considered to be non-response (composite variable strategy). Participants who die due to COVID-19 will be treated as missing (hypothetical strategy).

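### For the primary endpoint, the 10-event subgroup rule leaves 'event' undefined and sets no minimum for non-responders or for either arm, so small categories can be modelled with no finite treatment odds ratio

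*SAP*

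**What the plan says.** SAP 4.2.2.6 analyses the primary endpoint (normokalaemia at day 180) by age, sex, country, heart failure, diabetes, RAASi use, CKD stage, absence of a CKD diagnosis, two groupings of baseline potassium, and length of index stay. Each category gets its own logistic model, specified by reference to SAP 4.2.2.4, which includes treatment and "participant recruitment country as an independent variable". Six countries are listed. The only condition is "Subgroup analyses will only be conducted providing there are 10 or more events per subgroup category".

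The covariate-adjusted model in SAP 4.2.2.5 has a parallel rule: a covariate may enter "if there are more than 10 participants with an event in each level of the covariate".

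Neither section says whether an event is a response or a non-response. SAP 4.2.2.1 makes response (occurrence of normokalaemia) the dependent variable. SAP 4.2.2.1 and 4.2.2.3 count death, loss to follow-up, a missing Visit 10 assessment, rescue therapy and RAASi down-titration as non-response. Neither 4.2.2.5 nor 4.2.2.6 says what to do if a model separates.

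**The concern.** The information in a logistic model is limited by the rarer of the two outcomes. Here the modelled outcome is response, and the design expects most participants to respond. A rule that counts responders therefore counts the outcome that is usually plentiful. A category of 14 with 10 responders passes on 4 non-responders. If all 4 are in one arm, the maximum-likelihood treatment odds ratio is infinite. Up to five country parameters fitted to the same few non-responders make this more likely.

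For the main secondary endpoint the same sentence gates Cox models (SAP 4.2.3.7). There the event is the rarer outcome (17% v 43.2%, Protocol 9.2.2), so the count at least falls on the limiting side.

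In 4.2.2.5, a covariate level with 11 responders and no non-responder qualifies. That level's coefficient then has no finite estimate, although the treatment effect can still be estimated from the other levels.

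At stake are the subgroup results shown beside the primary result as evidence on consistency. An undefined term also leaves the rule to be settled at programming.

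**Working it through.** **Inputs.** Response 0.88 (SZC) and 0.59 (SoC), Protocol 9.2.1. Equal arms, since participants "will be randomised in a 1:1 ratio to one of the following arms" (Protocol 1.1). Post-randomisation dropout 20%, Protocol 9.2.1. Planned randomisation: "resulting in approximately 130 participants discharged and randomised". Six countries, SAP 4.2.2.6.

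**The plan's own figure.** Protocol 9.2.1 says its assumptions "yield a sample size of 36 participants per arm (total N = 72". With two-sided 5% and 80% power:

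n = [1.960 × √(2 × 0.735 × 0.265) + 0.842 × √(0.88 × 0.12 + 0.59 × 0.41)]² / 0.29² = 35.2, rounded up to 36 per arm. Then 72 / (0.8 × 0.8) = 112.5, or 113 enrolled. Both figures are reproduced. The plan gives no subgroup figure to reproduce.

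**Two scenarios.**
- Design rates: 0.88 v 0.59, mean 0.735.
- Planned dropout scored as non-response, equally in both arms: 0.88 × 0.8 = 0.704 and 0.59 × 0.8 = 0.472, mean 0.588.

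**Expected non-responders beside 10 responders.** Design: 10 × 0.265 / 0.735 = 3.6. With dropout: 10 × 0.412 / 0.588 = 7.0.

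**Without country (exact).** With N/2 = n per arm, let a and b be the responders in each arm, binomial with the rates above. A category passes if a + b ≥ 10. The odds ratio a(n − b) / [b(n − a)] has no finite logarithm if a or b equals 0 or n. The share reported is P(pass and no finite estimate) / P(pass).

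**With country (simulation).** Six equally likely countries with no true country effect. Passing categories were tested by linear programming for whether the treatment coefficient has a finite maximum-likelihood estimate. Ranges show the spread over repeated runs.

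Share of passing categories with no finite treatment odds ratio:

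| Category size | Design, no country | Design, country kept | Dropout, no country | Dropout, country kept |
|---|---|---|---|---|
| 14 | 54% | 75–78% | 28% | 58–64% |
| 20 | 28% | 44–49% | 4% | 20–21% |
| 24 | 22% | 36–38% | 1.5% | 12–13% |
| 30 | 15% | 21–22% | 0.5% | 5% |
| 40 | 8% | 11–12% | 0.1% | 0.5–1% |
| about 65 | 2% | 2% | 0% | 0% |

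**By-country subgroups.** The mean country has 130 / 6 = 22 participants. Country is constant within a country, so the no-country calculation applies: 25% at the design rates and 2% with dropout.

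**How often such categories pass.** At 14 participants, 70% pass at the design rates and 24% with dropout. The chance that a category of 14 both passes and has no finite estimate, without country, is 0.70 × 0.54 = 38% or 0.24 × 0.28 = 7%. With country kept and dropout scored, it is about 0.24 × 0.60 = 14%.

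**The case against.** The strongest case against is as follows.

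- **The SAP does not say that events are responders.** True. That reading is inferred from the dependent variable; the documented defect is the undefined term. If 'event' meant non-response, the total count would protect the rarer outcome, though still not each arm.
- **The design rates overstate the problem.** They come from a calculation for evaluable participants, with dropout added afterwards, whereas the full analysis set scores dropout as failure. Protocol 9.2.1 also says that RAASi down-titration is not in the rates and is expected to lower SoC response. This stands. With dropout scored, SoC response is below half, and categories of 24 average 9.7 non-responders.
- **The percentages are conditional on passing.** True. With dropout scored, the rule stops most categories of 14.
- **Category sizes are not in the documents.** True. No counts are given for CKD stage, age 85 and over, or potassium 6.0–6.5 mmol/L.
- **The consequence is limited.** Subgroups lie outside the testing order in SAP 3.3.4, and an infinite odds ratio is visibly uninformative. This stands as a limit on importance.

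A reader might infer that subgroup odds ratios will generally be infinite, or that passing categories typically have only two to five non-responders. The documents do not support either. With dropout scored, only 28% of passing categories of 12 to 22 participants have two to five non-responders (65% at the design rates), and halves of the trial are almost unaffected. Nor should the with-country figures be applied to the by-country subgroups.

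**Conclusion.** The concern holds in limited form. SAP 4.2.2.6 leaves 'event' undefined. On the natural reading it protects neither the less frequent outcome nor either arm, and it carries country into models that may rest on a handful of non-responders.

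The problem is material for passing categories of about 20 or fewer. It remains noticeable at 24 (about 37% at the design rates, 12% with planned dropout as non-response) and is negligible at about 65. The dropout scenario is closer to the SAP's own scoring, so the lower figures deserve at least as much weight as the higher ones.

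The figures assume responders are the events, 1:1 allocation within categories, six equally likely countries without a country effect, and dropout equal between arms. Unequal country shares gave similar results. The primary test and its type I error are untouched; what is affected is the subgroup evidence and, more mildly, the adjusted model in 4.2.2.5.

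**What to change.** In SAP 4.2.2.6, for the primary endpoint:

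1. Define 'event'.
2. Model a category only if it has at least 10 of the less frequent outcome, whether responders or non-responders, and both outcomes occur in each arm.
3. Fit subgroup models with treatment only. The presence of both outcomes in each arm then guarantees a finite odds ratio. Alternatively, keep country and state a penalised or exact fit for use if separation occurs.
4. Where the condition is not met, show n/N by arm without an odds ratio.

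In SAP 4.2.2.5, require both outcomes in every covariate level, or merge sparse levels. Requiring more than 10 of each would go too far: it could remove country, a term in the primary model, from the adjusted model.

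The cost is SAP wording and fewer subgroup odds ratios. Ten non-responders are expected in a category of 10 / 0.265 = 38 participants at the design rates, or 10 / 0.412 = 24 with dropout. A category of 22 would meet the 10-of-each count about 3% or 36% of the time respectively, so many by-country results would appear as n/N only.
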